2.3.3 Index hospitalization

The number and percentages of the following information about patients and their index hospitalization visit will be summarized by treatment group. The RS will be used.

- Patient in shock (No, Yes, Unknown)
- Patients receiving following treatment from index hospitalization to randomization
 - Vasopressor (No, Yes, Unknown)
 - Inotrope (No, Yes, Unknown)
 - Nitroprusside (No, Yes, Unknown)
 - Nesiritide (No, Yes, Unknown)
 - Patient cared for in Intensive Care Unit (ICU) (No, Yes, Unknown)

The number and percentage (categorical variables) and descriptive statistics (continuous data) for information on patient index hospitalization discharge will be summarized by treatment group. The RS will be used.

- Duration of index hospitalization stay in days [(*date:time of discharge date:time of arrival*)/(3600*24)]
- Discharge disposition (Home or with family/friends, Rehabilitation facility, Skilled nursing facility, Death, Unknown)
- Discharge weight (kg)
- New York Heart Association (NYHA) class (I, II, III, IV, Not done)
- Patient experienced worsening heart failure since randomization (No, Yes, Unknown)
- Patient cared for in ICU (No, Yes, Unknown)
 - Number of nights in ICU since randomization
- Patient treated with any of the following medication classes since randomization (Intravenous inotrope, Intravenous vasopressor, Nitroprusside, No, Unknown)
- Patient took third dose of double-blind study treatment (No, Yes)

All information relating to the index hospitalization will be listed.

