2.8.1.3 AE summaries

The following summary tables will be provided:

- AEs, regardless of study treatment relationship, by primary SOC, PT and worst severity
- Most frequent (\geq 5%) AEs, regardless of study treatment relationship, by PT
- AEs, suspected to be related to study treatment, by primary SOC and PT
- Serious adverse events (SAE), regardless of study treatment relationship, by primary SOC and PT
- SAEs, suspected to be related to study treatment, by primary SOC and PT
- SAEs occurring with a frequency of $\geq 0.5\%$, regardless of study treatment relationship, by PT
- SAEs, regardless of study treatment relationship, by primary SOC, PT and seriousness criteria
- AEs leading to discontinuation, regardless of study treatment relationship, by primary SOC and PT
- AEs requiring dose adjustment or study treatment interruption, regardless of study treatment relationship, by primary SOC and PT
- AEs requiring additional therapy, regardless of study treatment relationship, by primary SOC and PT

• Death resulting from AEs, regardless of study treatment relationship, by primary SOC and PT

2.8.1.4 In addition, an overview of TEAEs presenting the number of percentage of patients having at least one TEAE for each of the above categories will be provided.Adverse events of special interest / grouping of AEs

Separate summaries will be provided for AEs related to all angioedema, positively adjudicated angioedema, elevated creatinine, hyperkalemia and symptomatic hypotension. The summaries will be presented by primary SOC, PT and worst severity.

Additionally, a sensitivity analysis will be performed on the AEs of special interest for patients randomized to sacubitril/valsartan. The number and percentages of AEs of special interest occurring prior to the active dose of sacubitril/valsartan will be presented along with the number and percentages of AEs of special interest occurring on or after the active dose of sacubitril/valsartan during the double-blind phase. The following definition will be used:

Angioedema:

AE prior to active study treatment = if event occurred within 1 day of dosing as recorded on the Angioedema Assessment Visit 2 (randomization)

AE after active study treatment = if event occurred after 1 day of dosing as recorded on the Angioedema Assessment Visit 2 (randomization)

Symptomatic hypotension:

AE prior to active study treatment = First dose date \leq event \leq Third dose date of study treatment

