AE after active study treatment = *Third dose date of study treatment* \leq *event* \leq *Last dose date of double-blind medication*

Elevated creatinine and hyperkalemia:

AE prior to active study treatment = First dose date:time of study treatment \leq event \leq Third dose date:time of study treatment

AE after active study treatment = *Third dose date:time of study treatment* \leq *event* \leq *Last dose date:time of double-blind medication*

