5.1.2 AE date imputation

The following algorithm should be used to estimate start dates for which only partial information is known:

- Missing day and month
 - If the year is the same as the year of first study treatment, then the day and month of the start date of treatment will be assigned to the missing fields.
 - If the year is prior to the year of first study treatment, then December 31 will be assigned to the missing fields.
 - If the year is after the year of first study treatment, then January 1 will be assigned to the missing fields.
- Missing month only
 - Treat day as missing and replace both month and day according to the above procedure.
- Missing day only
 - If the month and year are the same as the year and month of first study treatment, then the start date of treatment will be assigned to the missing day.
 - If the month and year are before the year and month of first study treatment, then the last day of the month will be assigned to the missing day.
 - If the month and year are after the year and month of first study treatment, then the first day of the month will be assigned to the missing day.

If the imputed start date result is after the stop date (and the stop date is complete), the imputed start date will be reset to the stop date.

The following algorithm should be used to estimate stop dates for which only partial information is known:

- Missing year
 - Date left missing.
 - Missing month
 - Impute 'December'.
- Missing day

•

- Impute 'last date of that month'.

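### The before/after-active-dose split has no rule for patients who never took dose 3, and an onset dated only to the month or year of first dosing defaults to the placebo lead-in

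*SAP*

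**What the plan says.** SAP 2.8.1.4 states that "a sensitivity analysis will be performed on the AEs of special interest for patients randomized to sacubitril/valsartan". It asks for events before the active dose and events on or after it, during the double-blind phase. SAP 2.1.1 puts the start of active treatment in this arm at the third dose, because the first two doses are placebo.

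The two classes are defined by event type:

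- **Symptomatic hypotension**, by date: "AE prior to active study treatment = First dose date \leq event \leq Third dose date of study treatment", against "AE after active study treatment = *Third dose date of study treatment* \leq *event* \leq *Last dose date of double-blind medication".
- **Elevated creatinine and hyperkalemia**, by date and time. The earlier class is "First dose date:time of study treatment \leq event \leq Third dose date:time of study treatment"; the later class runs from "Third dose date:time of study treatment" to the last double-blind dose.
- **Angioedema**, by a form field. The earlier class applies "if event occurred within 1 day of dosing as recorded on the Angioedema Assessment Visit 2 (randomization").

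Three other places bear on these rules:

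- SAP 2.3.3 tabulates at index discharge "Patient took third dose of double-blind study treatment (No, Yes"), so a patient without dose 3 is foreseen.
- SAP 5.1.1 allows no imputation of study treatment dates.
- SAP 5.1.2 imputes partial event onset dates. If the known month and year match those of first treatment, "then the start date of treatment will be assigned to the missing day". If only the year is known and it matches, the first-treatment day and month are used.

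**The concern.** The split is there to separate events on the placebo lead-in from events on active sacubitril/valsartan. Two features work against that.

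First, both classes need a third-dose date. A patient who stops during the lead-in has none, and an event that ends dosing at that stage is exactly the kind the earlier class should capture. As written, the rules do not capture it.

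Second, moving an uncertain onset to the first-dose date is cautious when the question is whether an event is treatment-emergent. Here it is the opposite: it assigns to placebo an event that may have arisen on active drug.

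The lead-in lasts only a day or so and should hold few events, so one misplaced event could change how that row reads.

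**Working it through.** The plan states no figure for this split, so there is none to reproduce. The check applies the rules as written. Let D1 be the first dose, D3 the third dose, DL the last double-blind dose and e the onset.

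- *Prior*: D1 ≤ e ≤ D3
- *After*: D3 ≤ e ≤ DL

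**Step 1. No third dose.** D3 does not exist and may not be imputed (SAP 5.1.1). Neither inequality can be evaluated, so a hypotension, creatinine or hyperkalemia event has no class. Angioedema can still be classed, because its rule does not use D3.

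**Step 2. Partial onset dates, worked examples.** Protocol 5.5.4 places dose 3 on the second treatment day. Take D1 = 6 March 2017, D3 = 7 March and DL = 1 May.

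| True onset | Missing part | Imputed onset | Class |
|---|---|---|---|
| 27 March | day | 6 March | prior (wrong) |
| 10 April | day | 1 April | after (right) |
| 10 April | day and month | 6 March | prior (wrong) |

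**Step 3. How often this happens among affected dates.** The 5.1.2 rules were run over every first-dose date in 2017. Assumptions: D3 = D1 + 1 day, DL = D1 + 56 days, true onset uniform over the days after the third-dose date, and no effect of the stop-date reset.

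| Onset within, days of D1 | Day missing: prior only / after only / both | Day and month missing: prior only / after only / both |
|---|---|---|
| 7 | 85.2% / 11.5% / 3.3% | 98.8% / 1.0% / 0.3% |
| 14 | 73.7% / 23.0% / 3.3% | 97.8% / 1.9% / 0.3% |
| 28 | 50.7% / 46.0% / 3.3% | 95.9% / 3.8% / 0.3% |
| 56 | 25.0% / 73.2% / 1.8% | 92.1% / 7.7% / 0.3% |

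All these onsets truly follow the third-dose date, so every *prior only* entry is an error. Over the full 56 days, most day-missing events still go to *after*.

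For creatinine and hyperkalemia, no rule supplies a time for an imputed date. Its order against a dose time on the same day is therefore undefined.

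**Step 4. The shared bound.** With e = D3 both inequalities hold, so the event counts in both classes. For hypotension this covers the whole calendar day of dose 3. It also explains the *both* entries above. For example, with D1 = 31 March and D3 = 1 April, a day-missing April onset becomes 1 April and is counted twice.

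**Step 5. Illustrative size, not an estimate.** The arm has 882/2 = 441 patients. The lead-in is taken as 1.0 to 1.5 days out of 56, with a constant rate. Two hypotension rates from Protocol 1.1 are each treated, by assumption, as an 8-week incidence.

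- 18% (Table 1-1): 441 × 0.18 × 1.0/56 = 1.4, and 441 × 0.18 × 1.5/56 = 2.1 lead-in events.
- 8.4% to 9.7% (titration study): 441 × 0.084 × 1.0/56 = 0.7, and 441 × 0.097 × 1.5/56 = 1.1 lead-in events.

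If 1% to 5% of events lacked the day (assumed; no source in the documents), the 25% share from Step 3 gives misplaced events between 441 × 0.084 × 0.01 × 0.25 = 0.1 and 441 × 0.18 × 0.05 × 0.25 = 1.0.

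**The case against.** The best defence has four parts.

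**The governing sentence settles the first case.** The split asks for events before the active dose, and a patient who took none has only such events. This is a fair guide to intent, but the operative definitions do not implement it and a programmer would have to decide. It also does not settle a late event in someone long off treatment, which is hardly a lead-in event.

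**SAP 5.1.2 may not govern these events.** SAP 2.1.1 lists symptomatic hypotension separately from adverse events, SAP 2.8.4.2 describes dedicated episode variables, and the clock-time rules suggest laboratory data. This stands, and it is why the second half of the point is conditional on the rule being applied. The lead-in is also spent in hospital, so missing days there are less likely; but the displaced events are those that arose later.

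**The figures are soft.** The 18% comes from a trial with 27 months' median follow-up, and the titration study's rates are about half that. The documents give no count of patients without dose 3 or of partial dates. This stands in full.

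**Little is at stake.** All adverse events are listed, and those leading to discontinuation have their own table. This also stands.

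Some stronger readings are tempting but not supported:

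- *All partly dated events go to the lead-in.* Only those whose known part matches first dosing do.
- *SAS sorts missing values lowest, so an event without dose 3 would be reported as after active drug.* The SAP shows no code for this split. The later class also requires onset no later than the last dose, and an event that stops dosing normally follows the last dose taken. That largely blocks this path, except mainly for hypotension dated on the last-dose day.
- *Patients without dose 3 inflate the later class's denominator.* SAP 2.8.1.4 states no denominator.
- *The SAP records that some patients missed dose 3.* A No/Yes item shows only that this was foreseen.

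**Conclusion.** The point holds within limits. For symptomatic hypotension, elevated creatinine and hyperkalemia, the rules leave events in patients without a third dose unclassified. This follows from the text alone.

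Where SAP 5.1.2 is applied, an onset dated only to the month or year of first dosing is assigned to the lead-in regardless of its true day. That is a stated rule giving an anti-conservative result for this purpose, and not just a missing detail. The shares in Step 3 rest on uniform onset and on dose 3 falling the day after dose 1.

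The number of patients or events affected cannot be computed from the documents. The only reading of size available is that the lead-in class may hold roughly 0.7 to 2.1 hypotension events under the assumptions in Step 5, so a single misplacement would be visible. The analysis is descriptive and confined to one arm. Neither the primary result nor any between-arm comparison changes. This is a worthwhile clarification of low severity.

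**What to change.** Amend SAP 2.8.1.4 as follows.

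- **(a) Patients with no active dose.** Identify them from the dose records, since the discharge item could miss a dose 3 taken after discharge. Report their events in a row labelled *prior to active / never received active*, so that late off-drug events are not presented as lead-in events. Leave these patients out of any denominator for the *after* class.
- **(b) Partial onset dates.** Do not use the SAP 5.1.2 imputed start date for this split. Class such an event as *prior* only if its stop date precedes the third dose. Otherwise show it as *timing unknown*, with a count under the conservative *after active* assignment.
- **(c) Shared bound.** Make one of the two inequalities at the third dose strict, for both the date and the date-and-time versions, so that no event is counted twice.

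The cost is a few sentences of SAP text and a small programming change. No new data are needed and no other table is affected.

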2.8.2 Deaths

Patient deaths will be summarized by total, primary cause of death, type of cardiovascular death and type of non-cardiovascular death and will be presented by study phase (see Section 2.1.1 for study phase definitions). A patient listing of all deaths with recorded principal cause of death will be provided. All patients in the FAS will be included for the above analysis.

2.8.3 Laboratory data

Laboratory values will be summarized using shift tables (from baseline to most extreme post baseline value) by each laboratory parameter at its worst severity by study phase (see Section 2.1.1 for study phase definitions). The number and percentage of patients with laboratory values

will be presented by low/normal/high (low and high) classifications to compare baseline to worst post baseline value.

In addition, laboratory values and the change from baseline for each parameter by visit will be summarized by treatment group and open-label sacubitril/valsartan. In the event that there are multiple laboratory values within a visit, the worst value will be summarized.

A separate summary table will be presented by study phase (see Section 2.1.1 for study phase definitions) with the number and percentage of patients having notable lab abnormalities based on percent change from baseline (see Section 5.3 for a list of notable laboratory abnormalities).

A summary of hyperkalemia labs by visit will also be presented by treatment group and openlabel sacubitril/valsartan. The highest potassium value for the event and any potassium re-test results will be descriptively summarized. Similarly, creatinine labs will also be presented by visit, treatment group and open-label sacubitril/valsartan. The highest creatinine value for the event and any creatinine re-test results will be descriptively summarized.

Listings of all laboratory values will be provided. Separate listings for hyperkalemia labs, creatinine labs and pregnancy tests will also be provided. Any notable laboratory abnormalities will also be flagged.

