3.2 Rationale of study design

Hospitalization for ADHF identifies patients at increased risk of death and re-hospitalization following discharge. This increased risk justifies intervention with novel treatment strategies initiated prior to hospital discharge to improve patient outcomes. Both the PARAMOUNT and PARADIGM-HF trials demonstrated reductions in the NT-proBNP compared to the comparator enalapril and valsartan, respectively, in both the chronic reduced ejection fraction and preserved ejection fraction heart failure patients. PARADIGM-HF demonstrated reductions in the NT-proBNP values seen at both 4 weeks and 8 months post randomization in the arm receiving the combination of the sacubitril/valsartan compared to the enalapril arm. In the current protocol, the primary endpoint of NT-proBNP will be evaluated at both the 4 and 8 week intervals to better assess the short-term benefit/risk ratio of sacubitril/valsartan compared to enalapril in patients who have been stabilized from an ADFH hospitalization in the setting of reduced ejection fraction.

The need for a 36-hour wash-out period is required per the FDA approved USPI label because there is a potential for increased risk for angioedema in patients who receive both an ACE inhibitor and the combination of sacubitril/valsartan. The requirement to stop the ARB is because there is an ARB contained within sacubitril/valsartan combination. The open-label period of 4 weeks provides the opportunity for every patient to receive sacubitril/valsartan and evaluate the change in NT-proBNP and other biomarkers in patients who had been previously receiving enalapril, while still being monitored for safety outcomes.

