2.1.1 General definitions

Study treatment

Patients will receive either sacubitril/valsartan or enalapril during the first 8 weeks of the study. Study treatment will refer to either of these two drugs.

Baseline

For safety labs and biomarkers, baseline is defined as the last non-missing assessment collected <3 hours from the first dose of study treatment, including matching placebos. For patients not treated, baseline is defined as the last non-missing assessment prior to or on the date of randomization. BNP and NT-proBNP values will be based on clinical laboratory samples processed and assessed by the central laboratory.

For other assessments, including those for which assessment time is collected (ECGs, HF Signs and Symptoms, and pregnancy tests), baseline is defined as the last non-missing assessment prior to or on the start date of study treatment (randomization date for patients not treated), including matching placebos.

Date of first administration of study treatment

Double-blind phase: The date of first administration of study treatment in the double-blind phase is defined as the first date a dose of study treatment is administered and recorded on the Dose Administration (Visit 2) electronic case report form (eCRF).

Open-label phase: The date of first administration of study treatment in the open-label phase is defined as the first date a dose of sacubitril/valsartan is administered in the open-label phase and recorded on the Dose Administration (Visit 7) eCRF.

Pooled phase: The date of first administration of study treatment in the pooled phase is defined as the first date a dose of sacubitril/valsartan is administered either in the double-blind phase or open-label phase.

Date of last administration of study treatment

Double-blind phase: The date of last administration of study treatment in the double-blind phase is defined as the last date a dose of study treatment is administered in the double-blind phase and recorded on the Dose Administration (Visit 7) eCRF, or earlier if prematurely discontinued and recorded on the Early Investigational Product Permanent Discontinuation eCRF.

Open-label phase: The date of last administration of study treatment in the open-label phase is defined as the last date of sacubitril/valsartan is administered in the open-label phase and recorded on the Drug Administration eCRF.

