Patients who died, withdrew consent, or were lost to follow-up prior to or on their projected Week 8 visit date will be excluded from the open-label phase.

Pooled phase

An assessment during the pooled phase is defined as any assessment obtained in the doubleblind phase for patients randomized to sacubitril/valsartan, or any assessment obtained in the open-label phase regardless of randomized treatment arm.

Last contact

The date of last contact will be determined from the Date of Last Contact field on the Study Completion/Exit eCRF.

Year, month and week

For reporting purposes, the rules below will be followed to convert a year, month and week to days.

1 year = 365.25 days

1 month = 30.3475 days

1 week = 7 days

1 day = 24 hours

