2.8.4.2 Vital signs

All vital signs (systolic and diastolic blood pressure [mmHg], pulse rate [sitting/beats per minute], weight [kg], height [cm], BMI [kg/m²] and waist/hip circumference) will be descriptively summarized at each visit by treatment group and open-label sacubitril/valsartan. Change from baseline will also be presented.

A separate summary table will be presented with the number and percentages of patients having notable vital signs based on changes relative to baseline values (see Section 5.4 for a list of notable vital signs) by study phase (see Section 2.1.1 for study phase definitions).

The number and percentages of patients having symptomatic hypotension will also be summarized by study phase. The following variables associated with symptomatic hypotension will also be presented: symptoms occurring while standing, any treatment or medication change as a result of episode, lowest documented systolic blood pressure, systolic blood pressure position, lowest documented diastolic blood pressure and diastolic blood pressure position. A listing for symptomatic hypotension will also be presented.

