2.12 Biomarkers

BNP and NT-proBNP will be collected and descriptively summarized by visit, treatment group and open-label sacubitril/valsartan. Values and the change from baseline for each parameter will be summarized by visit, treatment group and open-label sacubitril/valsartan. Analyses will be based on the FAS. BNP and NT-proBNP values will be based on clinical laboratory samples processed and assessed by the central laboratory.

Additional biomarker measurements believed to be relevant to the pathophysiology of the disease processes of heart failure and dysfunction will also be collected and summarized by visit, treatment group and total. These may include, but no limited to those assessing cardiac and renal benefit or biomarkers related to the study treatment mechanism of action such as:

- Neurohormones BNP and NT-proBNP
- hs-Troponin T

Additional analysis of biomarkers is discussed in Sections 2.5, 2.7 and 2.13.

Biomarker samples from patients who withdrew consent will not be analyzed by the central laboratory.

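### Open-label and pooled sacubitril/valsartan safety changes use the in-hospital baseline, so for enalapril switchers they mix change on enalapril with change after the switch

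*SAP*

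**What the plan says.** SAP 2.1.1 gives one baseline rule per data type. For safety laboratory values and biomarkers it is the "last non-missing assessment collected <3 hours from the first dose of study treatment, including matching placebos". For other assessments, which cover vital signs, it is the "last non-missing assessment prior to or on the start date of study treatment (randomization date for patients not treated), including matching placebos". The same section describes study treatment as the drug taken in the first eight weeks. Protocol 9.2 also ties baseline to the first dose of randomized medication.

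SAP 2.1.1 places everything after the Week 8 visit in the open-label phase. The pooled phase combines double-blind assessments of the sacubitril/valsartan arm with "any assessment obtained in the open-label phase regardless of randomized treatment arm".

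SAP 2.8.3 reports laboratory shift tables by study phase, as well as the "number and percentage of patients having notable lab abnormalities based on percent change from baseline". SAP 2.8.4.2 reports, again by study phase, patients "having notable vital signs based on changes relative to baseline values". Both sections also summarize change from baseline by visit, with an open-label sacubitril/valsartan column.

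**The concern.** For a patient randomized to enalapril, the open-label phase is a one-way switch. Exposure to sacubitril/valsartan starts only after Week 8, but the reference value was taken during the heart failure admission. An abnormality that arose on enalapril and persists is then counted in the open-label and pooled sacubitril/valsartan columns. A real change after the switch can go unseen if the value had moved the other way by Week 8. Recovery from decompensation adds a further shift. Patients are admitted with fluid overload (Protocol 4.1), so a weight change of more than 7% from the in-hospital value may partly reflect decongestion.

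At stake is the attribution of safety changes to a drug in tables labelled with that drug's name.

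**Working it through.** No figure in the documents is in dispute, so there is none to reproduce. The check is mainly textual, with arithmetic to show direction and possible size.

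**1. Is there a second baseline?** SAP 2.1.1 defines a first-administration date for each phase, so its baseline wording might be read as phase-specific. Three features point to a single double-blind baseline: the reference to matching placebos, the fallback to the randomization date for untreated patients, and Protocol 9.2. No visible text sets a Week 8, open-label or pooled baseline.

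**2. Exposure and change run on different clocks.** SAP 2.1.1 and 2.4.1 start pooled exposure at the first sacubitril/valsartan dose in any phase. For a switcher that is after Week 8. The change set against that exposure starts about eight weeks earlier.

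**3. What the tables report for a switcher.**

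Reported change = (randomization to Week 8, on enalapril) + (Week 8 to open label, on sacubitril/valsartan)

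The sum is on the absolute scale for blood pressure and on the log scale for percent changes. Only the second term falls after the switch.

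**4. Invented patients under the thresholds of SAP 5.3.2 and 5.4.1.**

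| Measure and rule | Randomization | Week 8 | Open label | From randomization | From Week 8 |
|---|---|---|---|---|---|
| Creatinine, rise >50% | 1.0 | 1.45 | 1.55 | 1.55/1.0 - 1 = +55%, flagged | 1.55/1.45 - 1 = +7%, not flagged |
| Creatinine, rise >50% | 1.6 | 1.0 | 1.55 | 1.55/1.6 - 1 = -3%, not flagged | 1.55/1.0 - 1 = +55%, flagged |
| SBP, fall >20 mmHg | 110 | 130 | 108 | 108 - 110 = -2, not flagged | 108 - 130 = -22, flagged |

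The absolute limit of SBP below 90 mmHg would not catch the third patient either.

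**5. Possible frequency, on assumed inputs.** The documents give no variability for creatinine or SBP change. The illustration assumes that sacubitril/valsartan has no effect, that the changes before and after Week 8 are normal and independent, and that there is one open-label value per switcher. Let s1 and s2 be the SDs before and after Week 8, and Φ the normal distribution function.

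- Creatinine, log scale. From randomization: 1 - Φ((ln 1.5 - ln(1 + drift)) / √(s1² + s2²)). From Week 8: 1 - Φ(ln 1.5 / s2). Example with drift 0, s1 = 0.15, s2 = 0.10: 0.405/0.180 = 2.25, giving 1.2%; from Week 8, 0.405/0.10 = 4.05, giving 0.003%.
- SBP. From randomization: Φ((-20 - drift) / √(s1² + s2²)). From Week 8: Φ(-20 / s2).

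| Rule | Assumed s1; s2; mean drift to Week 8 | Flagged from randomization | Flagged from Week 8 |
|---|---|---|---|
| Creatinine rise >50% | 0.15-0.25; 0.10-0.15; 0 to +20% | 1.2%-22.2% | 0.003%-0.34% |
| SBP fall >20 mmHg | 12-16; 10-12; -10 to +10 mmHg | 2.7%-30.9% | 2.3%-4.8% |

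The width of these ranges comes from the assumptions. They show that the effect need not be trivial; they are not estimates for this trial.

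**6. Is a pre-switch value available?** Yes. Chemistry is drawn at Visits 7 and 9 (Protocol 6.5.5.2), and vital signs are taken at every visit (Protocol 6.5.2).

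**The case against.** **The tables are descriptive and secondary to the trial's aims.** Protocol 9.5.3 rules out inference on safety data, and the safety objectives cover the eight double-blind weeks. This stands: no test, power figure or stated objective is touched.

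**The scope is narrow.** Adverse events, deaths, symptomatic hypotension and absolute vital-sign limits use no baseline. Scheduled hematology stops at Visit 7, and Week 10 chemistry is a limited panel. This stands too. Listings of all values would also let a careful reader trace an early onset, but a reader of the summary table would not see it.

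**Change from randomization is a legitimate cumulative summary, and without a control group a Week 8 reference cannot separate drug from time.** Both are true. The first is a reason to keep the existing summary beside a new one. The second limits what the new one can prove, but at least the enalapril period is no longer counted in it.

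**A split by former arm may exist in table shells that are not public.** Possible. The SAP document history states such a split for demographic and baseline tables; nothing visible states one for the safety tables.

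**Stronger readings that the documents do not support.** Protocol 3.2 says that the open-label period serves to "evaluate the change in NT-proBNP and other biomarkers in patients who had been previously receiving enalapril", and SAP 2.12 says "Values and the change from baseline for each parameter will be summarized by visit, treatment group and open-label sacubitril/valsartan". A reader might infer that this purpose goes unanswered. That cannot be concluded: SAP 2.12 refers further biomarker analysis to Section 2.13, which is not visible and may use a Week 8 reference. A reader might also infer that the NT-proBNP fall is overstated. On the planning figures the ratio to randomization is 0.95 × 0.82 = 0.78, against 0.82 from Week 8 in switchers if the effect is fully reached. These are two different quantities, each correct under its own label.

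**Conclusion.** The point holds on the visible text. For enalapril-randomized patients, laboratory shift tables, percent-change laboratory flags, change-based vital-sign flags and by-visit changes after Week 8 combine two treatment periods under a sacubitril/valsartan label. The pooled baseline also does not match the pooled exposure start. Events can be falsely counted or missed.

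The effect is confined to descriptive, change-based chemistry and vital-sign summaries. The primary and secondary endpoints are unaffected, and nothing is claimed about exploratory NT-proBNP analyses. The conclusion rests on reading SAP 2.1.1 as one double-blind baseline. If that wording can be read per phase, it still needs clarifying so that programmers apply one rule. The likely frequency is unknown. The change is worth making because it is cheap, not because a trial conclusion depends on it.

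**What to change.** Add a phase-specific baseline to SAP 2.1.1 and refer to it in 2.8.3 and 2.8.4.2:

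- **Open-label tables:** for both former arms, use the last available value before the first open-label dose, normally Week 8, and show results by randomized arm.
- **Pooled tables:** use the last value before the first sacubitril/valsartan dose. That keeps the in-hospital baseline for the sacubitril/valsartan arm and gives Week 8 for enalapril switchers. Show these by randomized arm as well, because the two references come from different clinical settings.
- **Cumulative view:** keep the existing change from randomization, labelled as such.

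The cost is SAP wording and extra programming; no new data are needed. Where Week 8 is missing, an earlier double-blind value must serve. For scheduled chemistry that is Week 4, since Protocol Table 6-1 has none at Week 6. The pooled column will mix in-hospital and outpatient references, which the split by arm makes visible but does not remove.
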